8.6. Endpoints

8.6.1. Safety

Safety monitoring will be undertaken using in-person symptom surveillance, symptom diaries, and targeted physical exams. Solicited adverse event monitoring will survey and specifically inquire about symptoms listed in section 11.6.2. Abnormalities will be described in detail in order to monitor progress. This will include the name of the adverse event, the date and time of onset and offset (duration), severity, and Principal Investigator determination of relationship to the investigational vaccine. Safety monitoring labs will also be performed on Days 8, 29, and 50. Clinical outcomes will be prospectively defined and actively surveyed during the study. The study procedures are detailed in Table 8.

Clinical definitions will be used to grade the severity of symptoms in accordance to the severity scale included in section 11.8.3.

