11.8.3. Severity Assessment

All AEs will be assessed for severity by the investigator. The investigating team will execute the investigator severity scale below. Inherent in this assessment is the medical and clinical consideration of all information surrounding the event including any medical intervention required. Each event will be assigned one of the following categories: mild, moderate, severe, or potentially life-threatening. See section 11.5.2 for vital signs and section 11.5.4 for laboratory values for further guidance in the assignment of severity. The following criteria may be used for any symptom not included in the grading scale. The eCRF for AEs will reflect only the highest severity for continuous days an event occurred.

Mild

Grade 1

Does not interfere with routine activities

Moderate	Grade 2	Minimal level of discomfort Interferes with routine activities
Severe	Grade 3	Moderate level of discomfort Unable to perform routine activities
Potentially life-threatening	Grade 4	Significant level of discomfort Hospitalization or ER visit for potentially life-threatening event

FDA guidelines for toxicity will be followed; however, if a subject is evaluated in an emergency room for a non-life-threatening illness or symptoms (i.e., visits emergency department on weekend for mild problems because the physician's office is closed), the information from that visit will be reviewed, and severity of the AE will be assessed according to the subject's clinical signs and symptoms.

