8.3. Adverse Events

The primary objective of this study is safety of the Invaplex_{AR}-DETOX vaccination. All summaries of adverse events will be presented by vaccine dose (1 to 3) and overall, and by treatment group. Safety summaries and analyses will be presented for the Safety Population.

Local and general (systemic) solicited AEs, as well as lymph node assessments, are collected within 30 minutes of each vaccine dose and through 7 days following each dose (day of vaccination and subsequent 7 days). Lymph nodes are assessed as palpable or not palpable and for tenderness (yes/no). All other solicited events and symptoms are graded as 0 (normal), 1 (mild), 2 (moderate), 3 (severe), and 4 (potentially life-threatening). All general and local reactions are listed below.

Local Reactions:

- Site pain, site tenderness, swelling, induration, site redness and pruritus.

General Reactions:

- Fever, nausea, vomiting, abdominal pain, diarrhea (loose stools), appetite change, fatigue, headache, myalgias, arthralgias and malaise.

Adverse events will be summarized by MedDRA[®] system organ class (SOC), preferred term (PT), severity (mild, moderate, severe, potentially life-threatening) and whether related (definitely, probably or possibly) or not related (unrelated, unlikely) to study product. When calculating the incidence of adverse events (i.e., on a per subject basis), each subject will only be counted once per category. Per protocol, all adverse events occurring within 28 days of the third vaccination (Day 71) will be presented ([Table 18, Appendix A](#) and [Listing 10, Appendix C](#)). All events reported on the adverse event CRF will be included in the listing.

To assess safety, the number and percentage of subjects experiencing at least one AE, and the number and percentage of subjects experiencing each specific AE, categorized by body system, preferred term and product administered (for individual post-dose periods and for the entire study period) along with exact 95% CIs, will be tabulated. Overall summaries by study group include the number and percentage of subjects experiencing: (1) any adverse experience; (2) any Grade 2 or greater AE; (3) any AE judged related to study product; (4) any Grade 2 or greater AE judged related to study product; (5) Any SAE; (6) Any SAE related to IP.

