Table 22: Subjects Experiencing AEs Related to Study Product Up to and Including Visit 11 (Day 28 Post-Dose 3), by MedDRA® Preferred Term (PT), Severity and Treatment Group - Safety Population [In-Text, by PT only].....	47
Table 23: Subjects Experiencing AEs Post-Dose 1 and Prior to Dose 2, by MedDRA® System Organ Class (SOC), Preferred Term (PT), Severity and Treatment Group - Safety Population	47
Table 24: Subjects Experiencing AEs Related to Study Product, Post-Dose 1 and Prior to Dose 2, by MedDRA® System Organ Class (SOC), Preferred Term (PT), Severity and Treatment Group - Safety Population.....	47
Table 25: Subjects Experiencing AEs Post-Dose 2 and Prior to Dose 3, by MedDRA® System Organ Class (SOC), Preferred Term (PT), Severity and Treatment Group - Safety Population	47
Table 26: Subjects Experiencing AEs Related to Study Product, Post-Dose 2 and Prior to Dose 3, by MedDRA® System Organ Class (SOC), Preferred Term (PT), Severity and Treatment Group - Safety Population.....	47
Table 27: Subjects Experiencing AEs Up to 28 Days Post-Dose 3, by MedDRA® System Organ Class (SOC), Preferred Term (PT), Severity and Treatment Group - Safety Population	47
Table 28: Subjects Experiencing AEs Related to Study Product, Up to 28 Days Post-Dose 3, by MedDRA® System Organ Class (SOC), Preferred Term (PT), Severity and Treatment Group - Safety Population.....	47
Table 29: Grade 2 or Greater Non-Serious Adverse Events [In-Text]	48
Table 30: Deaths, Serious Adverse Events and Other Significant AEs [In-Text]	48
Table 31: Hematology and Serum Chemistry Test Results, Descriptive Statistics by Treatment Group - Safety Population	49
Table 32: Final On Therapy Hematology and Serum Chemistry Severity Grading, by Treatment Group and Relationship ¹ to IP - Safety Population.....	50
Table 33: Vital Signs: Descriptive Statistics by Visit and Treatment Group - Safety Population	51
Table 34: Summary of Abnormal Physical Exam Findings Prior to Dose 1 – Safety Population	52

A.1 Demographics Tables**9.1 Overall Study Design and Plan Description****Table 1: Study Design [In-Text]**

Cohort	Group	N	Route	Study Dose	Timing of Injections
A	A-1	16	IM	InvaplexAR-DETOX 2.5 µg	Day 1, 22, 43
	A-2	4	IM	Placebo	Day 1, 22, 43
B	B-1	16	IM	InvaplexAR-DETOX 10 µg	Day 1, 22, 43
	B-2	4	IM	Placebo	Day 1, 22, 43
C	C-1	16	IM	InvaplexAR-DETOX 25 µg	Day 1, 22, 43
	C-2	4	IM	Placebo	Day 1, 22, 43

IM = intramuscular.

Immunogenicity and Safety Measurements Assessed

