Table 19: Total Number of Adverse Events, Up to and Including Visit 11 (Day 28 Post-Dose 3), by MedDRA® System Organ Class and Preferred Term, and Treatment Group - Safety Population

MedDRA®		Invaplex _{XR} 2.5 µg (N=X)	Invaplex _{XR} 10 µg (N=X)	Invaplex _{XR} 25 µg (N=X)	Placebo (N=X)
System Organ Class (SOC)	Preferred Term (PT)	No. of Events	No. of Events	No. of Events	No. of Events
Any SOC	Any PT				
[SOC 1]	Any PT				
	[PT 1]				
	[PT 2]				
[SOC 2]	Any PT				
	[PT 1]				
	[PT 2]				

N=Number of subjects in the safety population.

Each row may include multiple events per subject, including repeats of the same AE within a subject.

The following table will have the same format as **Table 19**. Note that grouping is by PT only.

Table 20: Total Number of Adverse Events Related to IP, Up to and Including Visit 11 (Day 28 Post-Dose 3), by MedDRA® Preferred Term, and Treatment Group - Safety Population [In-Text - by PT only]

Table 21: Subjects Experiencing AEs, Up to and Including Visit 11 (Day 28 Post-Dose 3), by MedDRA® System Organ Class (SOC), Preferred Term (PT), Severity and Treatment Group - Safety Population

		InvaplexAR 2.5 µg (N=X)		InvaplexAR 10 µg (N=X)		InvaplexAR 25 µg (N=X)		Placebo (N=X)		
		n (%)	95% CI	n (%)	95% CI	n (%)	95% CI	n (%)	95% CI	P-Value b,c
Any SOC										
Any Preferred Term	Any Severity	x (xx.x)	(xxx, xx.x)	x (xx.x)	(xxx, xx.x)	x (xx.x)	(xxx, xx.x)	x (xx.x)	(xxx, xx.x)	(xxx, xx.x)
	Mild									
	Moderate									
	Severe									
	Life-Threatening									
[SOC 1]										
Any Preferred Term	Any Severity									
	Mild									
	Moderate									
	Severe									
	Life-Threatening									
[PT 1]										
	Any Severity									
	Mild									
	Moderate									
	Severe									
	Life-Threatening									
[PT 2]										
	Any Severity									
	Mild									
	Moderate									
	Severe									
	Life-Threatening									

N=Number of subjects in the Safety Population. CI=Exact (Clopper-Pearson) Confidence Interval.

AE = Adverse events (including SAEs and solicited AEs) that were reported at any time up to and including Visit 11 (28 days post-Dose 3).

a Subjects are only counted once per SOC/PT category, based on maximum severity over all AEs reported within each category.

b Pearson's Chi-square test or Fisher's exact 2-tailed test of any difference between groups in proportion of subjects with any event.

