c For statistically significant ($p<0.05$) p-values, significant pairwise differences will be based on non-overlapping 95% CIs.

The following tables will have the same format as [Table 21](#).

Table 22: Subjects Experiencing AEs **Related to Study Product** Up to and Including Visit 11 (Day 28 Post-Dose 3), by MedDRA® Preferred Term (PT), Severity and Treatment Group - Safety Population [In-Text, by PT only]

Table 23: Subjects Experiencing AEs Post-Dose 1 and Prior to Dose 2, by MedDRA® System Organ Class (SOC), Preferred Term (PT), Severity and Treatment Group - Safety Population

Table 24: Subjects Experiencing AEs **Related to Study Product**, Post-Dose 1 and Prior to Dose 2, by MedDRA® System Organ Class (SOC), Preferred Term (PT), Severity and Treatment Group - Safety Population

Table 25: Subjects Experiencing AEs Post-Dose 2 and Prior to Dose 3, by MedDRA® System Organ Class (SOC), Preferred Term (PT), Severity and Treatment Group - Safety Population

Table 26: Subjects Experiencing AEs **Related to Study Product**, Post-Dose 2 and Prior to Dose 3, by MedDRA® System Organ Class (SOC), Preferred Term (PT), Severity and Treatment Group - Safety Population

Table 27: Subjects Experiencing AEs Up to 28 Days Post-Dose 3, by MedDRA® System Organ Class (SOC), Preferred Term (PT), Severity and Treatment Group - Safety Population

Table 28: Subjects Experiencing AEs **Related to Study Product**, Up to 28 Days Post-Dose 3, by MedDRA® System Organ Class (SOC), Preferred Term (PT), Severity and Treatment Group - Safety Population

Table 29: Grade 2 or Greater Non-Serious Adverse Events [In-Text]

Treatment	Subject ID	Age at Onset (years)	Adverse Event	Previous Dose #	Onset Day (Duration)	Severity	Relationship to Study Treatment	Alternative Etiology	Action Taken with Study Treatment	Subject Discontinue d Due to AE	Outcome	Comments
[SOC 1]												
[PT 1]												
[PT 2]												
[SOC 2]												
[PT 1]												

[Rows will be sorted by SOC, PT, treatment group, subject, onset day]

Table 30: Deaths, Serious Adverse Events and Other Significant AEs [In-Text]

Similar format as Table 29. Additional information on each event may be provided in a narrative provided by the medical monitor.

A.3.2 Clinical Labs

Table 31: Hematology and Serum Chemistry Test Results, Descriptive Statistics by Treatment Group - Safety Population

		InvaplexAR-DETOX			Placebo
		2.5 µg	10 µg	25 µg	
WBC Count (10³/µL)					
Screening	N				
	Mean (SD)				
	Median				

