Listing 9: ALS IgG Antibody against *S. flexneri 2a* Invaplex

Study Group	Subject ID	Day -7		Baseline		Visit 03		Visit 06		Visit 09		Visit 11	
		Titer	Fold Rise	Titer	Fold Rise	Titer	Fold Rise	Titer	Fold Rise	Titer	Fold Rise	Titer	Fold Rise

C.3 Safety Listings

Listing 10: Adverse Events, by MedDRA System Organ Class (SOC) and Preferred Term (PT) [SOC1], [PT1]

Treatment Group	Subject ID	Adverse Event	Dose Number	Onset Day Post-Dose (Duration)	Severity	SAE	Relationship to Study Treatment	In Not Related, Alternative Etiology	Action Taken with Study Treatment	Subject Discontinued Due to AE?	Outcome
AE Summary/Comment:											

Listing 11: Clinical Lab Values – Hematology

Time Point ¹	Actual Study Day	Reference Range	Value	Change from Baseline	Severity	Clinically Significant	Comment
Subject ID: XXXXX, Treatment Group: YYYY							
[Parameter 1]							
Screening							
Day -7							
Day 8							
Day 29							
Day 50							
[Parameter 2]							
Screening							
Day -7							
Day 8							
Day 29							
Day 50							
[continue for other parameters]							

Listing 12: Clinical Lab Values – Chemistry

Similar format to Listing 11.

Listing 13: Vital Signs

Treatment Group	Subject ID	Time Point	Actual Study Day	Temperature (°C)	Systolic Blood Pressure (mm Hg)	Diastolic Blood Pressure (mmHg)	Heart Rate (beats/min)	Weight (kg)	Height (cm)

Listing 14: Concomitant Medications

Study Group	Subject ID	CM Number	Medication	Medication Start Day	Medication End Day	Ongoing at Study Start	Indication	Taken for an AE? (AE Description; Number)	Taken for a condition on Medical History? (MH Description; Number)	ATC Level 1 (ATC Level 2)

Listing 15: Pregnancy Report**Subject ID: XXXXX, Treatment Group: YYYYYY**

Maternal Information	
Pregnancy Number	
Date pregnancy reported	
Pregnancy test date	
Pregnancy status	
Estimated date of delivery	
Number of fetuses	
Actual date of delivery	
Maternal complications	
Action Taken with Study Product	
Study Status	
Comments	
Gravida and Para	
Gravida	
Pre-Term Birth	Extremely / Very early / Early / Late
Term Birth	Early / Full / Late / Post
Still Birth	
Abortion	Spontaneous / Miscarriage / Elective / Therapeutic
Major Congenital Anomaly with Previous Pregnancy?	
Live / Still Birth Outcomes (include only fields relevant to outcome)	
Fetus Number	
Pregnancy outcome	
Fetal Distress During Labor and Delivery?	
Delivery method	
Gestational Age at Live/Still Birth	
Size for Gestational Age	
Apgar Score, 1 minute	
Apgar Score, 5 minutes	

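### The AE form keeps one undated maximum grade per continuous episode, so SAP Tables 23-28 can show a grade reached after a later dose under an earlier one

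*Protocol*

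**What the plan says.** **Recording.** Protocol 11.8.3, repeated word for word in SAP 4.5.2: "The eCRF for AEs will reflect only the highest severity for continuous days an event occurred". Protocol 8.6.1 lists what is captured for each abnormality, including "the date and time of onset and offset (duration), severity, and Principal Investigator determination of relationship". That is one start, one end and one grade per event.

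**Reporting.** SAP 3.1.1 makes tolerability after each dose part of the primary objective. SAP 8.3 follows through: "All summaries of adverse events will be presented by vaccine dose (1 to 3) and overall, and by treatment group". Tables 23-28 break subjects down by severity within dose periods. Table 23 is titled "Subjects Experiencing AEs Post-Dose 1 and Prior to Dose 2", Table 25 "Subjects Experiencing AEs Post-Dose 2 and Prior to Dose 3", and Tables 27-28 run to 28 days after dose 3 with no stated start. All use the Table 21 layout, whose footnote reads: "Subjects are only counted once per SOC/PT category, based on maximum severity over all AEs reported within each category".

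**Laboratory data.** Protocol 8.6.1: "Safety monitoring labs will also be performed on Days 8, 29, and 50". SAP 3.2.1.1 defines the laboratory endpoint through laboratory-based AEs after each vaccination. Table 31 summarises values and changes by time point. Table 32 grades only the final on-therapy value. Listings 11 and 12 carry a severity for each subject at each draw.

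**The concern.** The tables ask for the grade in each dose period, while the AE form keeps one grade for the whole episode. Once the maximum is stored without its date, the AE dataset cannot show whether a severe grade was reached before or after the next injection.

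This matters because worsening on repeat dosing is something a first-in-human, three-dose study should be able to show, and Tables 23-28 are the only planned tables that give grade by dose. If a peak is credited to the wrong period, an event that escalated with a later dose can look like a severe first-dose reaction, or like two equally severe periods.

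**Working it through.** **1. The plan's own figure.** SAP section 5 gives a 95% CI of 0-21% for no events in 16 vaccinees. The exact two-sided (Clopper-Pearson) upper limit is 1 − 0.025^(1/16) = 20.59%, which rounds to 21%. The figure reproduces and is not in dispute.

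**2. Is there a rule that would prevent the problem?** Three kinds were looked for in the two documents.
- *Closing an event at the next dose, or opening a record when the grade rises:* none. SAP 3.3.1 says deterioration is recorded as an AE, but this follows text on pre-existing conditions and does not clearly cover an AE that is already open.
- *Dating the peak grade:* none.
- *Assigning an ongoing event to a dose period:* none. Table 29 has columns for the previous dose and the onset day, and Listing 10 for the dose number and the onset day after that dose. Both suggest placement by onset, but no sentence says so.

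**3. One subject under each reading.** Suppose a continuous AE is Grade 1 after dose 1 and reaches Grade 3 after dose 2. It is stored as one record with onset after dose 1 and Grade 3.

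| | After dose 1 | After dose 2 |
|---|---|---|
| What happened | Grade 1 | Grade 3 |
| Placed by onset | Grade 3 | not shown |
| Placed in every period touched | Grade 3 | Grade 3 |

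The post-dose 1 cell is wrong under both readings. The post-dose 2 cell is wrong only under the first. Placement by peak date is impossible from the AE record, because that date is not kept.

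**4. Size per subject.** With 16 vaccinees per dose level (Protocol Table 7), each such subject changes a cell by 1/16 = 6.25 percentage points.

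**5. Illustration under placement by onset.** Assume k of 16 subjects worsen to the higher grade only after the later dose. The number k is assumed; the documents give no rate. The later dose is shown as 0/16, 95% CI 0-20.59%, and the earlier dose carries the k subjects. The correct later-dose entry is:

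| k | Later-dose rate | Exact 95% CI |
|---|---|---|
| 1 | 6.25% | 0.16-30.23% |
| 2 | 12.50% | 1.55-38.35% |
| 3 | 18.75% | 4.05-45.65% |
| 4 | 25.00% | 7.27-52.38% |

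**6. What is unaffected.** Tables 18, 21 and 22 use each subject's maximum over the whole period to Day 71 (Table 18 also covers later follow-up), so where the peak fell among the doses does not change them.

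**The case against.** **Laboratory grades are kept elsewhere.** A reader might infer that a laboratory abnormality is stored only once. It is not: Listings 11 and 12 give a severity at each of Days 8, 29 and 50, so a rise in grade can be found by subject. This stands. What remains is that no planned table summarises those grades by post-dose draw.

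**Two abnormal draws need not be one event.** The documents do not say that abnormal results at consecutive scheduled draws form one continuous episode, and Protocol 11.5.4 allows extra specimens that could show resolution in between. This stands. Treating them as one episode is plausible, not prescribed.

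**Placement by onset is not written.** A reader might also infer that later doses will always look cleaner than they were. That needs placement by onset. The titles of Tables 23-26 can equally be read to include ongoing events, and the later dose would then show the peak. This stands against the stronger reading, but the earlier dose is overstated under both.

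**The reach is narrow.** Solicited symptoms are graded daily in a diary on the day of vaccination and the next 7 days. Doses are 21 days apart and injections normally alternate arms. Only an AE that runs unbroken across a dose date and then worsens is affected. This stands.

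**Other safeguards exist.** Under Protocol 8.10, two or more Grade 2 laboratory abnormalities judged related to vaccine pause the study for safety review, whatever the final tables show. That protects participants during the trial; it does not correct the by-dose tables.

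**The eCRF completion guidelines are not available here.** They are mentioned in Protocol section 14 and may contain a splitting rule. If so, the protocol and SAP should state it, since their present sentence says otherwise.

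**Conclusion.** The point holds as a mismatch between how AE severity is recorded and how it is to be reported. For an episode that spans a dose and worsens afterwards, the stated rule gives a wrong grade by dose under either natural way of programming Tables 23-28. The error is 6.25 percentage points of a vaccine group per affected subject.

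The conclusion assumes that no unseen guideline splits such episodes. How many subjects would be affected is unknown, and the intervals in the illustration show only what would happen at assumed counts. The documents do not support saying that worsening will necessarily be reported as a reaction to the earlier dose alone, or that laboratory worsening is lost. No stated figure in the plan is wrong. The correction is worth making because by-dose tolerability is part of the primary objective and the missing date cannot be recovered from the AE dataset later.

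**What to change.** - **Protocol 11.8.3 and SAP 4.5.2:** when an ongoing AE rises in grade after a later dose, record the date of the grade change, or open a linked record starting on that date. Align the eCRF completion guidelines.
- **SAP 8.3 and Tables 23-28:** state that each subject is counted at the worst grade reached within each post-dose interval, that an ongoing event counts in every interval it touches at the grade reached there, and where the interval for Tables 27-28 begins.
- **Laboratory data:** add a table of grade by treatment group at Days 8, 29 and 50, from the data already in Listings 11 and 12.
- **Overall tables (18, 21, 22):** leave on one maximum per subject.

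The cost is a few extra AE records or dated lines, one more table and slightly more programming. Splitting records would raise the event counts in Tables 19-20, so linked records should be counted there as one event. No clinical procedure changes.

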11.9. Reporting Adverse Events

The PI will report all AEs to the sponsor and the local IRB in the appropriate safety, annual, and/or final reports. The investigative team will prepare annual reports and final reports for submission to the FDA.

11.9.1. Reporting Serious and Adverse Events

Contact information for reporting SAEs and unanticipated problems is provided in Table 12.

11.9.1.1. Reporting to the Sponsor

All SAEs and unexpected AEs must be reported promptly (within 72 hours) to the sponsor, whether or not the event is considered related to the study product. Further, the investigator should comply with relevant study-site SOPs on reporting SAEs.

The information that the investigator will provide to the sponsor is specified in Table 13. The sponsor may request additional information for purposes of the study.

Table 12: Study Contacts for Reporting Serious Adverse Events

Sponsor's Medical Officer	[name] PATH [name] [contact] [contact] E-mail: [contact]
Institutional Review Board	Naval Medical Research Center Research Services Directorate Office of Research Administration [name] [name] [contact] [contact]

Research Monitor	[name] WRAIR [contact] E-mail: [contact]
Research Monitor (alternate)	[name] WRAIR [contact] E-mail: [contact]

Table 13: SAE Information to Be Reported to the Sponsor

Notification Method	Information to Be Provided
E-mail or Telephone (within 72 hours)	IND number, sponsor study number, name of the investigational product, and investigator name and contact number
	Subject identification number
	SAE, onset date, date of investigational product administration, severity, relationship, and subject's current status
AND	
E-mail or Fax	Cover sheet or letter
	Adverse event case report form
	Supplemental SAE report forms
	Concomitant medication case report form or a list of concomitant medications
	Medical record progress notes including pertinent laboratory/diagnostic test results

NOTE: When submitting SAE reports via e-mail, the subject line of each e-mail notification will read as follows:
SAFETY REPORT – IND # _____, Sponsor Study # _____, Subject# _____, Event Term: _____

To comply with regulations mandating sponsor notification of specified SAEs to the FDA within 7 calendar days, investigators must submit additional information as soon as it is available. The sponsor will report unexpected SAEs associated with the use of the drug to the FDA as specified in 21 CFR 312.32 (c).

Investigators must follow all relevant regulatory requirements as well as specific policy at each institution regarding the timely reporting of SAEs to the NMRC IRB, and the research monitor.

